10.4.4 SAFETY ANALYSES

The safety analyses population includes all randomized participants. These analyses will include those participants who have reported an adverse event as well as those who do not report an adverse event. The incidence of treatment emergent adverse events, type of adverse events, and frequency of withdrawals due to an adverse event will be summarized by treatment group. Appropriate statistical comparisons will be made between treatment groups in terms of 1) rates of adverse events, 2) discontinuation due to adverse events, and 3) side effect scales. Rates will be compared using time to event hazard analysis. Frequencies will be analyzed using the chi square or Fisher Exact test. The scales will be examined using non-parametric analyses when appropriate. This study is not powered as an equivalence study so the non-significance of differences between groups does not truly imply equivalence.

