9.5 Safety Analysis Methods

9.5.1 Adverse Events

Any AEs will be listed and summarized by system organ class and preferred event term. Summaries will include the number of individuals experiencing events over the duration of the study. These summaries will be created for all AEs and AEs by severity (mild or moderate vs. severe or greater). Summaries will be provided by treatment group. If models can be run, point and confidence interval estimates of the risk difference will be obtained by modeling the probability of experiencing at least one adverse event. The model is specified with the equation:

$$g(E(Y_{ij})) = \beta_0 + \beta_1 \text{Treatment}_{ij} + s_i + \varepsilon_{ij}$$

Where $g(E(\cdot))$ indicates the identity link function on the expected value of Y , Y_{ij} is the occurrence of an AE outcome (any AE, any SAE, and any related AE) in subject i , β_0 is the intercept, β_1 is the treatment group coefficients, s_i is a random subject effect, and ε_{ij} is the residual error term.

Point and confidence intervals for the difference in experienced AE proportion between treatment groups will be estimated with a generalized linear mixed model (GLMM), assuming a binomial distribution and identity link. GLMMs are a flexible generalization of the linear mixed effect model that allows response outcomes to have an error distribution other than the normal distribution (McCullagh, & Nelder, 1989). Statistical analysis modeling will be carried out utilizing SAS/STAT PROC GLIMMIX (SAS Institute Inc. 2017) with the general structure of the SAS code for this model is listed below:

```
proc glimmix data=anlyaedata;
  class patient treatment;
  model any_ae = treatment / link=identity dist=binomial;
  random int / subject=patient;
run;
```

A similar model will be run for the difference in proportion of withdrawn subjects due to adverse events between treatment groups. If the above specified models cannot be fit due to limitations of the study data, frequencies will be analyzed using chi-square test.

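### The SAP's adverse-event model carries a participant random effect that one yes/no record per person cannot support, and its chi-square fallback supplies no interval when an arm has no events

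*SAP*

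**What the plan says.** SAP 9.5.1 sets the target by "modeling the probability of experiencing at least one adverse event". Its outcome definition reads "is the occurrence of an AE outcome (any AE, any SAE, and any related AE) in subject i", and a similar model is planned for withdrawals due to AEs.

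The estimate and interval are conditional: "If models can be run, point and confidence interval estimates of the risk difference will be obtained". The code is "model any_ae = treatment / link=identity dist=binomial" followed by "random int / subject=patient". The accompanying equation has a random subject effect and also a residual error term.

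If fitting fails, the SAP says: "If the above specified models cannot be fit due to limitations of the study data, frequencies will be analyzed using chi-square test". It names no interval method for that case. Protocol 10.4.4 is wider on the test: "Frequencies will be analyzed using the chi square or Fisher Exact test". It does not name a risk-difference interval either.

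Three other places matter. SAP 9.2 and 9.5.1 require counts and proportions of participants with events by arm. SAP 7.1 keeps the discontinued high-dose arm in the initial models. SAP 7.7 treats all comparisons outside the primary and secondary tests as descriptive, with 95% intervals.

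**The concern.** There are two separate defects, and the fallback repairs neither.

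- **Random effect.** The target is a per-participant proportion, so each person contributes one binary value. A participant-level variance needs repeated values within a person. Without them it cannot be told apart from ordinary binomial variation. This does not depend on how common the event is.
- **Identity link with an empty cell.** If an arm has no events, its fitted risk is exactly zero. That is the edge of the parameter space, and the usual model-based standard error is not usable there.

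Comparing AE rates, severity and relatedness is the primary safety objective in SAP 3.1.1. Protocol 10.4.4 itself warns that a non-significant difference does not show equivalence. For uncommon serious events the interval is therefore the informative result: it shows how large an excess the trial can exclude. The plan leaves that interval undefined in the tables where it is most needed.

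**Working it through.** **Inputs.** 45 per arm (Protocol 10.5, SAP 6), 1:1 allocation, 95% intervals (SAP 7.7). The documents give no rate of serious AEs or overall AE withdrawal for this trial, so the event rates below are assumptions, equal in both arms unless stated.

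**Check of the 45-per-arm input.** SAP 9.5.1 states no figure of its own, so the check uses the power table in Protocol 10.5. The Walters arcsine formula is power = Φ(√(2n)·[arcsin√(p2 − 1/2n) − arcsin√(p1 + 1/2n)] − 1.96). With n = 45 it gives 0.560 for 5/45 vs 14/45 and 0.795 for 5/45 vs 17/45. Both match the table.

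**1. Participant variance.** With one record per person and an identity link, the likelihood depends only on the marginal risk P(Y=1) = E(p + s) = p, where s is the random effect with mean zero. Numerical integration at p = 0.1 and p = 0.4, with random-effect SDs of 0, 0.01, 0.02 and 0.03, returned 0.1 and 0.4 every time. The data carry no information on the variance.

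A Python emulation of the default pseudo-likelihood fit (not a SAS run) failed to converge for 3 vs 1, 5 vs 2, 13 vs 5, 20 vs 10 and 42 vs 40 events out of 45. It converged for 29 vs 23, but with a risk difference of 0.139 against the observed 6/45 = 0.133.

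**2. Chance of an arm with no events.** P(at least one empty arm) = 1 − [1 − (1 − r)^n]².

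| Assumed rate r | n = 45 | n = 67 |
|---|---|---|
| 1% | 1 − (1 − 0.636)² = 0.868 | 1 − (1 − 0.510)² = 0.760 |
| 2% | 1 − (1 − 0.403)² = 0.643 | 1 − (1 − 0.258)² = 0.450 |
| 5% | 1 − (1 − 0.099)² = 0.189 | 1 − (1 − 0.032)² = 0.063 |

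The n = 67 column is illustrative: half of the 135 cap, which Protocol 10.5 applies across all three originally planned arms.

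Protocol 2.3.1 gives single-reason discontinuation rates on XR-NTX of 3%, 2%, 1% and 0.3%, without placebo rates. At 3% against an assumed 1% the probability is 1 − (1 − 0.254)(1 − 0.636) = 0.729 (from unrounded inputs). Keeping the high-dose arm, whose size is not stated, makes an empty cell more likely still.

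**3. The fallback in sparse tables (45 per arm).**

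| Events | Pearson chi-square p | Fisher p | Smallest expected count |
|---|---|---|---|
| 4 vs 0 | 0.041 | 0.117 | 2.0 |
| 3 vs 0 | 0.078 | 0.242 | 1.5 |
| 0 vs 0 | not computable | 1 | – |

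For 4 vs 0, Pearson is 90·(4·45)²/(45·45·4·86) = 4.19, and Fisher is 2·C(45,4)/C(90,4) = 0.117.

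**4. A score-type interval fills the gap.** Newcombe 95% intervals for the risk difference exist for every table tried:

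- 0 vs 0: 0 (−0.079 to 0.079)
- 1 vs 0: 0.022 (−0.059 to 0.116)
- 3 vs 0: 0.067 (−0.023 to 0.179)
- 13 vs 5: 0.178 (0.011 to 0.336)
- 29 vs 23: 0.133 (−0.069 to 0.321)

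The method must be named in advance. For 4 vs 0, Newcombe gives −0.006 to 0.207 and Miettinen-Nurminen gives 0.006 to 0.208.

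**The case against.** The sponsor can fairly say the following.

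- **The interval was never unconditional.** This stands: the SAP foresaw that fitting might fail. It then names only a test, so the foreseen failure has no interval attached.
- **The safety result is not lost.** A reader might infer that the plan leaves no risk difference at all. The documents do not support that. Counts and proportions by arm are reported, and the point difference is a subtraction.
- **Not every AE outcome is rare.** A reader might extend the empty-cell problem to related AEs. Protocol 2.3.1 lists injection-site reactions at 65% vs 50% and nausea at 29% vs 11%, so any related AE is likely to be common. The empty-cell argument is aimed at serious AEs and AE withdrawals. Overall withdrawal could also exceed any single-reason rate.
- **The failure is not confined to rare events.** This stands too. The redundant random effect is a problem at any rate, and the zero-event probabilities do not measure it. Software may set the variance to zero and continue when both arms have events, and SAS may behave differently from the emulation.
- **Chi-square is permitted by the protocol.** Choosing one of two allowed tests is not a contradiction. It is still the less suitable one for sparse tables. The 4 vs 0 example straddles 0.05 and was chosen to illustrate; no decision rule depends on that p-value.
- **One record per participant is inferred.** The equation is subscripted ij, the layout of the analysis dataset is not described, and the code is offered as a general structure. However, several records per person would not estimate the stated proportion.

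**Conclusion.** Wrong as written, with limited reach. The random intercept does not belong in a model for one yes/no value per participant. That conclusion rests on reading the target as one record each, and on no particular software. An arm without events also leaves the identity-link model with no usable interval. At 45 per arm the chance of that is about 87%, 64% and 19% at assumed equal rates of 1%, 2% and 5%. At an illustrative 67 per arm it falls to about 45% at 2% and 6% at 5%. The non-convergence at moderate event rates is supporting evidence only, since it comes from an emulation.

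What is lost is the conditional interval, above all for serious AEs and AE withdrawals. The comparison is descriptive under SAP 7.7, and the primary efficacy analysis is not affected. The change should be made, but the trial's main conclusion does not turn on it.

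**What to change.** In SAP 9.5.1:

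1. Delete the random statement from the code, and the random subject effect and residual term from the equation.
2. For any AE, any SAE, any related AE and AE withdrawal, report the unadjusted risk difference with one 95% interval method named in advance that copes with zero cells. Miettinen-Nurminen and Newcombe are suitable examples.
3. Where a p-value is given for a sparse table, use Fisher's exact test, which Protocol 10.4.4 already allows.
4. State that the analysis dataset has one record per participant for each AE outcome.

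The cost is a few lines of SAP text and code, with no new data and no change to trial conduct. It should be settled before unmasking so that the interval method is not chosen after the counts are known.

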9.6 Adherence and Retention Analysis Methods

9.6.1 Buprenorphine and Norbuprenorphine Assays

Buprenorphine and its metabolite norbuprenorphine are assayed using liquid chromatography tandem mass spectrometry by a commercial laboratory at weeks 8 and 12. Processed blood samples to quantify and compare the amount of buprenorphine and norbuprenorphine at weeks 8 and 12 by treatment group will be evaluated using an independent group T-test.

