7.5 PROHIBITED MEDICATIONS, TREATMENTS, AND PROCEDURES

Due to the potential drug: drug interactions (e.g., opiates) or confounding therapeutic effects (e.g., naltrexone or acamprosate), participants may not use the medications listed in the table below, unless authorized by PASA medical monitor and approved by the lead PIs.

PROHIBITED MEDICATIONS		
Opioids		
Abstral, Actiq, Duragesic, Fentora, Onsolis (fentanyl)	Exalgo (hydromorphone hydrochloride)	Oxycet, Percocet, Roxicet, Xartemis XR (oxycodone/acetaminophen)
Anexsia, Co-Gesic, Hycet, Lorcet, Lortab, Liquicet, Maxidone, Norco, Vicodin, Xodol, Zolvit, Zydome (hydrocodone/ acetaminophen)	Hycodan, Hydromet (hydrocodone/ homatropine)	Percodan (oxycodone/ aspirin)
Avinza, Kadian (morphine sulfate)	Hysingla (hyrocodone)	Rezira (hydrocodone/ pseudoephedrine)
Butrans (buprenorphine)	Ibudone, Reprexain, Vicoprofen	Targiniq ER (oxycodone/ naloxone)
Demerol (meperidine)	Morphabond, Oramorph, Roxanol-T, Sublimaze (morphine)	TussiCaps and Tussionex, Vituz (hydrocodone/ chlorpheniramine)
Dilauidid, Zohydro ER (hydromorphone)	Nucynta ER (tapentadol)	Tylenol #3 and #4 (codeine/ acetaminophen)
Dolophine, Methadose (methadone)	Oxaydo, Xtampza ER (oxycodone)	Zutripro (hydrocodone/ chlorpheniramine/ pseudoephedrine)
Embeda (morphine/ naltrexone)	OxyContin, Palladone (oxycodone hydrochloride)	
Medications Used to Treat AUD		
Antabuse (disulfiram)	Revia (naltrexone hydrochloride)	
Campral (acamprosate)	Vivitrol (extended-release naltrexone as a non-study drug)	
Medications Thought to Effect ETOH Consumption		
Gablofen, Lioresal (baclofen, muscle relaxant)	Topamax (topiramate; also listed under mood stabilizer)	
Zofran (ondansatrin; prevents nausea and vomiting)		
Stimulants and/or ADHD Treatment		
Adderall (amphetamine, dextroamphetamine)	Dexedrine (dextroamphetamine)	Vyvanse (lisdexamfetamine)

PROHIBITED MEDICATIONS		
Desoxyn (methamphetamine)	Ritalin, Concerta (methylphenidate)	
Antipsychotics (except for quetiapine that may be used for insomnia)		
Benperidol (benperidol)	Mellaril (thioridazine)	Saphris or Sycrest (asenapine)
Clozaril, FazaClo, Versacloz (clozapine)	Moban (molindone)	Serentil (mesoridazine)
Geodon (ziprasidone)	Navane (thiothixene)	Stelazine (trifluoperazine)
Haldol (haloperidol)	Orap (pimozide)	Trilafon (perphenazine)
Invega (paliperidone)	Prolixin (fluphenazine)	Vraylar (cariprazine)
Latuda (lurasidone)	Risperdal (risperidone)	Zyprexa, Zydis (olanzapine)

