10.4.5 ADHERENCE AND RETENTION ANALYSES

To assess medication adherence, blood samples collected at study Week 8 and Week 12 will be tested for buprenorphine and its metabolite, norbuprenorphine, using quantitative assessments. We will also incorporate a self-report medication adherence CRF that will be completed at each study visit. Results of pill counts will be summarized over time by treatment group.

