4 STUDY METHODS

4.1 Overall Study Design and Plan

This randomized, double-blind, placebo-controlled, multi-site study evaluates the efficacy of SL-BUP combined with XR-NTX in the treatment of comorbid AUD and PTSD. Recruitment is based on convenience sampling of treatment-seeking veterans and active duty service members. Following screening and baseline visits, eligible patients are randomization to receive one of two treatments in a double-blind fashion for 12 weeks:

- Treatment A (SL-BUP 2mg and XR-NTX 380mg) or**
- Treatment B (SL-PLC and XR-PLC).**

The treatment allocation ratio for the treatment vs. placebo (PLC) regimens is **1:1** and is stratified by site, presence of concomitant antidepressants, and gender using a random permuted block scheme with variable block size (see below Figure). The study population will consist of ~ 90 Veterans with combat-related PTSD and co-morbid AUD. Detailed eligibility criteria for participant inclusion in this study are included in Section 4.2, below.

Study Design: RCT of KOR Antagonist in the treatment of Comorbid AUD and PTSD

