6 SAMPLE SIZE DETERMINATION

The sample size for a proof-of-concept study should be large enough to be able to detect a drug effect or surrogate signal, but at the same time expose a minimum number of subjects to an experimental drug combination in a reasonable timeframe within a restricted budget. Sample size was determined based on sample sizes used in similar double-blind, placebo-controlled studies of PTSD and AUD, and based on the estimated recruitment rate over the allotted enrollment timeline. With these factors in mind, we plan to enroll approximately 180 participants to allow screen failures/drop-out prior to randomization of approximately 90 participants across three sites (45 in each treatment arm) within a 24-month enrollment period. We estimate that attrition will be approximately 30%. However, all randomized participants will remain in analysis (intent-to-treat) regardless of how long they participate in the study.

For the primary outcome, we assumed the following success rates based on a similar previous study: Placebo arm 5/45 (11%) or less and 2mg BUP/NLTRX arm 17/45 (38%) or greater. We calculated power for two by two contingency tables for comparison of the treatment and Placebo arm using a Fisher's Exact test with the Walters approximation applying a nominal two-sided alpha level of 0.05. We observe power of 80% or greater for the above assumptions. In addition, a situation with more positive responses in the active treatment arm or fewer positive responses in the placebo arm would increase apparent power.

For secondary outcomes, we estimate that we will have >80% power to detect a medium effect size (Cohen's $f=0.25$, two-sided alpha level of 0.05) at 8 weeks. Under optimal conditions, where the correlation between consecutive observations on the same participant is high, and the variability observed between pairs of time points is fairly constant, fewer participants would be required (see table below). Under a less than ideal, worst-case situation where correlation between measurements is low and the variability observed between pairs of time points changes, the proposed sample size is still large enough to detect a moderate effect size, even after accounting for screen failures and drop-outs.

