8.3 Study Drug Exposure and Adherence

A dosing/pill count log will record the doses given each week (or since the last in-person visits) and whether the doses were distributed and taken per protocol. A descriptive table of overall dosing will be provided along with a listing of missed doses and reasons for the missed doses. To assess medication adherence, blood samples collected at study weeks 8 and 12 will be tested for buprenorphine and its metabolite, norbuprenorphine, using quantitative assessments. Results will be summarized graphically (box-plots) over time for the active treatment study group.

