Phosphatidyl ethanol (PEth)	Continuous (range between 0 and >210 ng/mL)	
Phosphatidyl ethanol (PEth) are a series of abnormal phospholipids located in the cell membrane and formed in the presence of ethanol and phospholipase D. PEth serves as a biomarker of alcohol ingestion in the past 2-3 weeks using liquid chromatography tandem mass spectrometric assessment of human blood (whole or dried spots). PEth in blood is often used as a marker of chronic alcohol use and was collected at baseline and weeks 8 and 12.
 
At the present time, the international scientific community has not yet established a cut-off value for PEth concentration in blood to be used for differentiating an acceptable social ethanol intake (<40 g for males and <20 g for females, according to the WHO parameters), from an at-risk-alcohol-use (40–60 g/die) and chronic excessive drinking behavior (>60 g/die). However, per LabCorp, PEth levels in excess of 20 ng/mL are considered evidence of moderate to heavy ethanol consumption.

Safety Outcomes		
Adverse Events	Counts and proportions	Total number and proportion of treatment emergent adverse events. Comparison of AE rates by treatment group will also be stratified by type and severity.
Withdrawals due to Adverse Events	Proportion	Proportions of individuals by treatment group who withdrew from the study due to adverse events
Adherence and Retention Outcomes		

Variable	Type	Definition
Serum Buprenorphine and Norbuprenorphine	Continuous	
Buprenorphine and its metabolite norbuprenorphine are assayed using liquid chromatography tandem mass spectrometry by a commercial laboratory. Sample results are available via the commercial laboratory portal using a study specific username/password combination and the unique participant code/requisition number.
 
To assess medication adherence, blood samples collected at study weeks 8 and 12 will be tested for buprenorphine and its metabolite, norbuprenorphine, using quantitative assessments.

Pill Count	Count and proportion	
A dosing log case report form (CRF) is completed weekly (or since the last in-person visit) for each participant. The number of completed NTX injections received (at baseline, week 4, and week 8) is recorded, as well as the number of missed SL-BUP pills per week. For each medication (NTX and SL-BUP), the proportion of subjects who missed any treatment will be derived, as well as the total number of missed injections or pills, per participant.

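### The between-arm t-test of serum buprenorphine in SAP 9.6.1 shows only that some active participants took tablets; it does not estimate how many did.

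*SAP*

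**What the plan says.** Protocol 10.4.5 gives the purpose of the assay: "To assess medication adherence, blood samples collected at study Week 8 and Week 12 will be tested for buprenorphine". SAP 9.2 repeats it in the outcome table: "To assess medication adherence, blood samples collected at study weeks 8 and 12 will be tested for buprenorphine and its metabolite". SAP 9.6.1, under the adherence and retention methods, states the analysis: buprenorphine and norbuprenorphine "at weeks 8 and 12 by treatment group will be evaluated using an independent group T-test". SAP 8.3 adds one further summary of the serum data: "Results will be summarized graphically (box-plots) over time for the active treatment study group".

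The comparator is "Treatment B (SL-PLC and XR-PLC" (SAP 4.1), that is, a placebo tablet and a placebo injection. Non-study buprenorphine is on the prohibited list in Protocol 7.5 ("Butrans (buprenorphine").

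Other adherence information is planned:
- SAP 8.3: a dosing and pill-count log, a descriptive dosing table and a listing of missed doses with reasons.
- SAP 9.6.2: the proportion missing any treatment, and missed pills and injections per visit by arm.
- SAP 5.2: a per-protocol set requiring the baseline and Week 4 injections and 80% of dispensed buprenorphine pills through Week 8. Serum level is not part of that definition.

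Neither document states a reporting limit for buprenorphine, an expected level, or a proportion of participants expected to be positive.

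**The concern.** The analysis does not answer the question it is listed under. If every placebo level is zero, the null hypothesis of equal means is the hypothesis that the active-arm mean is also zero. Rejecting it shows that some active participants had drug in serum. It does not say whether they were a quarter of the arm or nearly all of it.

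This matters because the trial is a proof of concept for the combination of buprenorphine and naltrexone. Injections are given and recorded by clinic staff (Protocol 6.1.10), but the tablets are taken at home, with up to a four-week supply dispensed at once (Protocol 6.1.5). Intake is otherwise tracked by pill count and a self-report form. The urine screen leaves out buprenorphine to protect the mask (Protocol 7.2.1). Serum is therefore the only biological check on tablet intake, and the plan neither quantifies the proportion positive nor compares it with the pill counts that define the per-protocol set.

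**Working it through.** The documents give no power, SD or adherence target for this t-test, so there is no figure of the plan's own to reproduce.

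**Inputs from the documents**
- SAP 6 plans "randomization of approximately 90 participants across three sites (45 in each treatment arm"), so 45 per arm.
- The same section says "We estimate that attrition will be approximately 30" per cent. Samples per arm: 45 × 0.70 = 31.5, taken as 31.
- Tests are two-sided (SAP 7.1). The 0.05 level is stated for the primary test and is assumed here for the serum test.

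**Assumed, because the documents give no assay figures**
- A proportion q of the active arm are takers, with log-normal levels of log-SD 0.8. The coefficient of variation is c = √(exp(0.8²) − 1) = √(exp(0.64) − 1) = 0.95.
- Non-takers and all placebo participants have level zero.

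**Step 1: the test statistic.** With takers' mean scaled to 1, the active-arm mean is q and its variance is q(1 + c²) − q². The placebo arm contributes zero to both, so typically

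t ≈ √n · q / √(q(1 + c²) − q²).

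For n = 31 and 1 + c² = exp(0.64) = 1.896:
- q = 0.20: 5.568 × 0.20 / √(0.379 − 0.040) = 1.114 / 0.583 = 1.91
- q = 0.30: 5.568 × 0.30 / √(0.569 − 0.090) = 1.670 / 0.692 = 2.41
- q = 0.50: 5.568 × 0.50 / √(0.948 − 0.250) = 2.784 / 0.836 = 3.33

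**Step 2: probability of p<0.05.** Skewed data make this approximation unreliable for tail probabilities, so they were simulated (Welch test, 31 per arm).

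| Takers in active arm | Probability of p<0.05 |
|---|---|
| 20% | about 0.60 |
| 30% | 0.89 |
| 40% | 0.97 |
| 50% | 0.99 |

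The pooled t-test is slightly higher. With all 45 per arm sampled, 30% takers gives 0.98.

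**Step 3: sensitivity to the assumed spread** (pooled t, 31 per arm).
- CV 0.3 to 1.0: 0.13 to 0.34 at 10% takers, 0.61 to 0.87 at 20%, 0.89 to 0.99 at 30%, and 0.97 to 1.00 at 40%.
- CV 1.5: 0.75 at 30% and 0.89 at 40%.

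**Step 4: the smallest count that is significant.** If all takers have the same level, 4 of 31 (13%) gives mean 0.129, variance 0.116 and t = 0.129 / √(0.116/31) = 2.11, pooled p = 0.039. The rank-test fallback allowed by SAP 7.1 gives p = 0.042 for 4 of 31, so it does not cure the problem.

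**Step 5: what a proportion would show instead** (31 sampled, exact 95% CI).
- 8/31 = 26% (12% to 45%)
- 25/31 = 81% (63% to 93%)

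These intervals do not overlap. With equal levels in takers, the t-test is significant in both cases (p = 0.002 and p < 0.001).

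**The case against.** The strongest reply is that the adherence question does not rest on this t-test.

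- **Box plots.** SAP 8.3 plots serum levels for the active arm alone. If fewer than half have drug and the rest are at zero, the median sits at zero; at 30% takers the lower quartile does too. A reader might infer that the plan could never tell an ineffective drug from untaken tablets. The documents do not support that: gross non-adherence would be visible in the planned figure. What is missing is a stated proportion with an interval.
- **Other measures.** A reader might also infer that serum is the only objective adherence measure. That is too strong for the combination, because injections are given and recorded by staff. It holds for tablets only in the sense of a biological check; returned tablets are counted, but a count does not prove ingestion.
- **Weight.** SAP 7.7 treats comparisons outside the primary and secondary tests as descriptive. Nothing in either document says that p<0.05 will be read as adequate adherence, and no population or efficacy result depends on it.
- **Skewness.** SAP 7.1 provides for normality checks, transformation or non-parametric tests. That answers a complaint about distribution but, as Step 4 shows, not the complaint about the question asked.
- **Certainty.** Significance with few takers is probable, not assured. At 10% takers it is unlikely with 31 per arm.

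All of this limits the consequence. None of it makes a between-arm t-test an estimate of adherence. A proportion detectable at two visits has its own limit: it does not measure intake over the whole dosing period, which is why it should be read beside the pill counts.

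**Conclusion.** The point holds as a minor one. SAP 9.6.1 names a method that cannot answer its stated purpose: the null is rejected with high probability once roughly a quarter to a third of the active arm have drug in serum, and almost always at half. The figures of about 60%, 89% and 99% (at 20%, 30% and 50% takers) rest on 31 samples per arm, log-SD 0.8 and zero levels in non-takers. Very variable levels, or fewer than about 20% to 25% takers, weaken them. The gap is the absence of a proportion positive and of any comparison with pill count. The primary, component and safety analyses are unaffected.

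The two-arm reading of the t-test is itself an inference. SAP 5.1 keeps participants randomized to the removed 8 mg arm in the ITT population, and SAP 9.6.1 does not say how a two-group test would treat them.

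**What to change.** In SAP 9.6.1, replace the t-test with:

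- the number and proportion, with exact 95% CI, of sampled active-arm participants whose buprenorphine or norbuprenorphine is at or above the laboratory's reporting limit, at Week 8 and at Week 12, with that limit stated in the SAP;
- a cross-tabulation of that result with pill-count adherence, using the 80% threshold already in SAP 5.2;
- the number of randomized participants with no sample at each visit;
- former 8 mg participants shown separately;
- a listing of any detectable level in the placebo arm as possible dispensing error or non-study use.

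Keep the box plots in SAP 8.3.

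The cost is a few lines of SAP text and one small table. No new samples are needed, and under Protocol 7.2.4 the results already go to the data coordinating center so that sites stay masked. Label: free improvement.
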